#### 9.4.6.2 CONTINUOUS ENDPOINTS

Summary statistics will be provided by visit and treatment arm. A by-subject listing will be presented for each assessment, by visit. Mixed model for repeated measures (MMRM) method for longitudinal continuous data will be used for testing, with treatment group as main effect, with visit and interaction of treatment by visit as factors, and with baseline values and stratification factor (Hurley Stage at baseline [Stage II or III]) as covariates.

### 9.4.7 ANALYSIS OF THE EXPLORATORY ENDPOINTS

Following are the exploratory endpoints:

- Change from Baseline in AN count at visits other than Week 16
- Percent change from Baseline in AN count at visits other than Week 16
- Proportion of subjects achieving AN50 and AN75 responses
- Percentage of subjects experiencing flare, defined as a  $\geq 25\%$  increase in AN count with an absolute increase in AN count of  $\geq 2$  relative to Baseline at each visit
- Change from Baseline in abscess count at each visit
- Change from Baseline in inflammatory nodule count at each visit
- Change from Baseline in draining fistula count at each visit
- Proportion of subjects achieving HiSCR50 at visits other than Week 16
- Proportion of subjects achieving HiSCR75 at each visit
- Proportion of subjects achieving 0 (inactive) or 1 (almost inactive) on HS-PGA at each visit
- Proportion of subjects with  $\geq 2$ -point reduction from Baseline on HS-PGA at each visit
- Change from Baseline in HS-PGA
- Change from Baseline in calculated composite of abscesses, draining fistulas, and inflammatory and non-inflammatory nodules
- Change from Baseline in HS Pain NRS at visits other than Week 16
- Percent change from Baseline in HS Pain NRS at visits other than Week 16

- Proportion of subjects achieving a  $\geq$  3-point reduction on the HS Pain NRS for subjects with Baseline HS Pain NRS of at least 3
- Proportion of subjects requiring rescue medication or treatment at each visit
- Change from Baseline in DLQI score at each visit
- Change from Baseline in IHS4 at each visit
- Change from Baseline in HiSQoL at each visit
- Change from Baseline in HS-PtGA at each visit
- Proportion of subjects in each response category for the HS-PtGA at each visit
- Proportion of subjects in each response category for the PGIC at each visit
- Proportion of subjects achieving improvement (“Much better” or “Very much better”) according to the PGIC at each visit
- Proportion of subjects achieving improvement (“A little better”, “Much better” or “Very much better”) according to the PGIC at each visit
- Proportion of subjects in each response category for the PGIB at each visit
- Change from Baseline in PGIB at each visit
- Proportion of subjects achieving “A little bothered” or “Not at all bothered” for the PGIB at each visit
- Proportion of subjects in each response category for the PGIS at each visit
- Proportion of subjects achieving “Mild” or “No activity” according to the PGIS at each visit
- Change from Baseline in PGIS at each visit
- Proportion of subjects in each category of Hurley Stage at each visit
- Change from Baseline in Hurley Stage at Weeks 16, 32, and 40
- Proportion of subjects achieving at least a 1-stage improvement in Hurley stage
- Skin tape strip and drainage fluid biomarkers analysis including, but not limited to, IL-36 and Th-17
- Presence of ADAs to imsidolimab
- Serum concentration following imsidolimab administration and other parameters as appropriate will be determined to describe the PK profile of imsidolimab

Methods for analyzing the above categorical and continuous efficacy endpoints will mirror the methods described in [Section 9.4.6.1](#) and [9.4.6.2](#), respectively. ITT analysis set will be used for analysis of exploratory efficacy endpoints.

As further additional exploratory analyses, the primary efficacy endpoint, all secondary efficacy endpoints, and some of the exploratory endpoints will be summarized using the Extension analysis population.

#### 9.4.8 SAFETY ANALYSES

Following are the primary safety and tolerability endpoints:

- Assessment of AEs, SAEs, and AEs leading to treatment discontinuation and study withdrawal.
- Vital signs.
- 12-Lead ECG.
- Clinical safety laboratory tests (hematology, biochemistry, and urinalysis).

All safety analyses will be performed on the Safety Analysis Set. In addition, the safety data for the subjects who entered the extension period will also be analyzed by the Extension Analysis Set.

#### 9.4.8.1 ADVERSE EVENTS AND SERIOUS ADVERSE EVENTS

A TEAE is defined as:

- A new event that occurs during or after first dose of study treatment or,
- Any event present at Baseline that worsens in either intensity or frequency after first dose of study treatment.

Adverse events will be coded using the MedDRA and only TEAEs will be summarized. Number of events and percentage will be tabulated by preferred term (PT) and primary system organ class (SOC). Multiple occurrences of an AE for a subject will only be counted once per primary SOC and PT. Percentages will be determined relative to the subjects in the Safety Analysis Set for the given treatment arm.

If the intensity or seriousness of the AE changes, the overall intensity or seriousness will be the maximum intensity or seriousness of the multiple occurrences. The TEAEs, SAEs, TEAEs leading to treatment discontinuation, and TEAEs leading to withdrawal of subject will be tabulated for each treatment arm.

All AE data will be listed for each subject.

Summaries over SOC and PT of TEAEs, TEAEs leading to death, SAEs, and TEAEs that led to discontinuation from the study or study treatment will be presented by treatment. Summaries will also be presented by relatedness to the study treatment and the severity of the TEAE.

#### 9.4.8.2 12-LEAD ELECTROCARDIOGRAM, VITAL SIGNS, AND CLINICAL SAFETY LABORATORY TESTS

Summaries and listings of data for vital signs and safety laboratory tests result (hematology, biochemistry, and urinalysis) will be presented. Appropriate descriptive statistics will be summarized for the observed value at each scheduled assessment and for the corresponding change from Baseline.

For hematology and biochemistry tests, listings of subject data will also flag up any abnormal or out-of-range values. Clinically significant changes in the laboratory test parameters will be summarized and listed. Hematology and biochemistry data will be reported in System International units.

Descriptive statistics will be used to present the safety outcomes including, weight, BMI, 12-Lead ECG, vital signs, and clinical laboratory test results.

Change from Baseline will also be summarized for vital signs, and clinical laboratory tests results.

All ECG data results (normal/abnormal) will be summarized using frequency and percentage, and parameter values will be summarized descriptively. Clinically significant abnormalities will be presented in by-subject listings.

#### 9.4.9 PHARMACOKINETIC ANALYSES

Limited imsidolimab PK analysis will be evaluated by assessment of drug concentrations in serum. These drug concentrations will be listed and summarized for each sampling time point using appropriate descriptive statistics. Due to limited PK sampling, noncompartmental analysis (NCA) will not be conducted in this study.

##### 9.4.9.1 DERIVATION OF PHARMACOKINETIC PARAMETERS

Due to limited PK sampling, NCA will not be conducted in this study. Thus, PK parameters will not be derived.

##### 9.4.9.2 PHARMACOKINETIC CONCENTRATION DATA ANALYSIS

A subject listing of all concentration-time data following SC injections will be presented by subject and scheduled sample collection time.

Concentration data of imsidolimab will be summarized by day and nominal time point using the number of observations, arithmetic mean, SD, CV, minimum, median, maximum, and geometric mean.

Graphs for mean concentration-time data following SC administration will be presented. Individual subject concentration-time plots will also be presented.

Mean trough concentrations-time data will be graphically displayed for samples collected at the visits specified in the SoA ([Section 1.3](#)) to visually assess time to attainment of steady state. Time to steady state may also be explored by using inferential statistics, if deemed appropriate. Other presentations of data may be added at the discretion of the PK scientist, as appropriate, and will be described in detail in a separate analysis plan.

##### 9.4.9.3 PHARMACOKINETIC PARAMETER DATA ANALYSIS

No analysis will be performed on PK parameters.

##### 9.4.9.4 POPULATION PHARMACOKINETICS ANALYSIS

Pharmacokinetic data from the study may also be used for population PK and/or exposure-response analyses. The data may be combined with PK data from other ANB019 studies, if

needed, to conduct the population PK analysis. If done, a separate analysis plan will be prepared, and results will be reported separately from the Clinical Study Report.

#### 9.4.9.5 IMMUNOGENICITY ANALYSES

Observed values for ADA levels/status will be listed by-subject and summarized with descriptive statistics based on the Safety Analysis Set. If data permits, potential correlation may be analyzed between ADA levels, serum concentration, and safety and efficacy endpoints.

In addition, ADA incidences (overall, treatment-emergent, and treatment-boosted) will be listed and summarized.

#### 9.4.10 BIOMARKER ANALYSES

Tape strip biomarkers (including but not limited to IL-36R and Th-17 cytokine) analysis will be performed by a third party designated by AnaptysBio. A separate analysis plan will be created for the biomarker analyses.

#### 9.4.11 PLANNED INTERIM ANALYSIS

Interim analyses (IA) may be performed for assessment of all primary and secondary efficacy endpoints, and evaluation of all safety data available.

The rationale for these analyses is to assist in making decisions for potential future development of this treatment. No adjustments to the current protocol are planned as a result of the interim analyses; therefore, overall alpha in the analyses of the primary analysis is expected to be maintained at 0.10, two-sided.

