## 9 STATISTICAL CONSIDERATIONS

### 9.1 STATISTICAL HYPOTHESES

The primary analysis for this study is to compare the mean AN count for imsidolimab with placebo during the double-blind treatment period, at a two-sided alpha = 0.10 level. Any testing being performed for secondary or exploratory endpoints will be considered exploratory in nature based on a 2-sided alpha = 0.10

$H_0: \mu_{\text{imsidolimab}} - \mu_{\text{Placebo}} = 0$  vs.  $H_A: \mu_{\text{imsidolimab}} - \mu_{\text{Placebo}} \neq 0$

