### 9.2 SAMPLE SIZE DETERMINATION

Approximately 120 subjects will be randomized in a 1:1:1 ratio to receive one of the following study treatments:

1. Imsidolimab 400 mg on Day 1 followed by 200 mg on Days 29, 57, and 85
2. Imsidolimab 200 mg on Day 1, followed by 100 mg on Days 29, 57, and 85
3. Placebo on Days 1, 29, 57, and 85

For this phase 2 study, the sample size was chosen empirically. Assuming a total of 10% of subjects will discontinue prior to Week 16, there will be approximately 108 evaluable subjects (36 subjects in each arm) at the end of Week 16. The study has 80% power to detect a between-group treatment difference of 4.9 lesions in the primary endpoint of mean change from Baseline in the AN count at Week 16, using a two-sided, equal-variance two-sample t-test at the  $\alpha = 0.10$  level, with the assumption of a common standard deviation (SD) of 8.2 lesions. The assumption was based on PIONEER 1 study (Kimball 2016). Table 6 shows more information on power from a set of scenarios of variability and between-group mean differences.

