#### 9.4.5 ANALYSIS OF THE PRIMARY EFFICACY ENDPOINT

The primary efficacy endpoint is the change from Baseline in AN count at Week 16.

The primary estimand, comprising four components, is defined as follows:

- a) The target population consists of subjects with hidradenitis suppurativa who are eligible to be included in the clinical trial based on the inclusion/exclusion criteria in the protocol. The ITT analysis set will include all randomized subjects. For the analysis, treatment will be assigned based upon the treatment arm to which subjects are randomized regardless of which treatment they receive.
- b) The primary variable is the change from baseline in AN count of an individual subject at Week 16.
- c) To handle intercurrent events such as use of rescue medications, the hypothetical strategy for estimand will be used. Data collected following receipt of rescue medication (if any) will be considered missing in the analysis.
- d) The population-level summary measures will be the population mean differences in the primary variable between each dose of imsidolimab and placebo at Week 16.

A general linear mixed effects model for repeated measures (MMRM) analysis will be used to estimate the least squares means (LSM) and associated standard errors for the change from Baseline in AN count to Week 16. The model will include change from Baseline in AN count at Week 16 as the dependent variable, fixed effects for treatment arm, categorical time point, and the treatment by time point interaction, and the Baseline AN count and stratification factor (ie, Hurley Stage at baseline (Stage II or III)) as covariates. An unstructured covariance structure will be used. The difference between LSMs (imsidolimab – placebo) at Week 16 will be presented along with the associated 90% CI and p-value. The ITT analysis set will be used for the primary efficacy analysis.

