### 3.3 Hypothesis Testing

The primary analysis for this study is to compare the mean change from baseline in AN count for imsidolimab vs. placebo at Week 16 of the double-blind treatment period, at a two-sided alpha = 0.10 level. The following hypothesis test will be done separately for each imsidolimab dose arm.

$$H_0: \mu_{\text{imsidolimab}} - \mu_{\text{placebo}} = 0 \text{ vs. } H_A: \mu_{\text{imsidolimab}} - \mu_{\text{placebo}} \neq 0$$

Treatment comparisons may be performed for the secondary or exploratory endpoints and will be considered exploratory in nature. Two-sided p-values and 90% confidence intervals will be produced.

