### **3.5 Sample Size**

The primary efficacy endpoint is the change from baseline in AN count at Week 16. The null hypothesis ( $H_0$ ) to be tested is that the mean change from baseline in AN count is the same for imsidolimab and placebo. This will be tested separately for each imsidolimab dose arm. Assuming a common standard deviation (SD) of 8.2, and a 10% dropout rate, an enrollment of 40 subjects (leaving 36 after dropout) in each of imsidolimab treatment arms and 40 subjects (leaving 36 after dropout) in the placebo arm will have at least 80% power to detect the overall treatment effect for a two sample t-test using a 2-sided significance level of  $\alpha=0.10$ , where the difference in the mean change from baseline between the imsidolimab and placebo group is assumed to be 4.9. The common standard deviation assumption was based on the PIONEER 1 study (Kimball 2014). No adjustments to  $\alpha$  are needed in this study for primary analysis or multiple comparisons.

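### The 0.10 alpha holds for each dose-versus-placebo comparison, not overall: with two unadjusted primary tests the chance of at least one false positive is about 0.175 (about 0.088 for false benefit)

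*Protocol*

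**What the plan says.** Four places bear on the point.

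- **Protocol 9.1** writes a single hypothesis. The primary analysis is to "compare the mean AN count for imsidolimab with placebo during the double-blind treatment period, at a two-sided alpha = 0.10 level". It does not say how the two regimens enter.
- **Protocol 9.4.5, item (d) of the estimand**, does separate them. The summary measures are the "population mean differences in the primary variable between each dose of imsidolimab and placebo at Week 16".
- **SAP 3.3** sets the level, "at a two-sided alpha = 0.10 level", and then states: "The following hypothesis test will be done separately for each imsidolimab dose arm". **SAP 3.5** repeats that each dose arm is tested separately, and says that no adjustments to alpha "are needed in this study for primary analysis or multiple comparisons". It gives no reason.
- **Protocol 9.4.11**, on interim analyses, says that "overall alpha in the analyses of the primary analysis is expected to be maintained at 0.10, two-sided". The reason offered is that the interim results will not lead to changes in the protocol.

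Neither document gives a testing order, a Dunnett or Bonferroni correction, or any other procedure linking the two primary tests. Neither says that 0.10 is meant as a per-comparison level. SAP section 8, which lists departures from the protocol, is silent on alpha.

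**The concern.** The plan contains two primary tests, each at 0.10, sharing one placebo arm. The protocol nevertheless attaches 0.10 to the overall alpha of the primary analysis, and the SAP says multiple comparisons call for no adjustment. Read together, these tell the user of the results that 0.10 is the false-positive rate of the primary analysis as a whole. For two unadjusted tests it is not.

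This matters because of how the results will be used. Under SAP 3.4 the unblinded Week 16 results go to executive management to support decisions on further development. Someone who takes 0.10 as the overall rate will underrate the chance that one of the two regimens looks effective by luck. The primary analysis is also the one place where an alpha statement carries weight, because Protocol 9.1 and SAP 3.3 label all secondary and exploratory testing as exploratory.

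**Working it through.** **Inputs**

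- Two primary tests, each two-sided at 0.10 (SAP 3.3; Protocol 9.4.5(d)).
- Allocation: "Approximately 120 subjects will be randomized in a 1:1:1 ratio" (Protocol 9.2), so about 40 per arm and one shared placebo arm.
- Dropout: "Assuming a total of 10% of subjects will discontinue prior to Week 16" (Protocol 9.2), leaving 36 evaluable per arm, 108 in all.
- Difference 4.9 lesions, common SD 8.2 (Protocol 9.2; SAP 3.5).

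**1. Reproduce the plan's own figure.** The noncentrality for one comparison is 4.9 / (8.2 × √(2/36)) = 4.9 / 1.933 = 2.535. The normal approximation gives power Φ(2.535 − 1.645) = 81.3%; the noncentral t on 70 df gives 80.7%. The stated 80% reproduces, and 36 / 0.90 = 40 per arm agrees with the planned enrolment. All 24 power cells of Protocol Table 6 also reproduce to within one point. The sample size is therefore a per-comparison calculation at 0.10, and it is correct as such.

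**2. Correlation of the two tests.** With n per arm, each difference from placebo has variance 2σ²/n. The two differences share the placebo mean, so their covariance is σ²/n. The correlation is (σ²/n) / (2σ²/n) = 0.5.

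**3. Chance of at least one significant result if neither dose works.** With c = 1.645 and ρ = 0.5,

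P(at least one) = 1 − ∫ φ(x) [Φ((c − √ρ·x)/√(1−ρ)) − Φ((−c − √ρ·x)/√(1−ρ))]² dx.

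| Method | Result |
|---|---|
| Bivariate normal | 0.1755 |
| t with pooled variance, 108 − 3 = 105 df | 0.1751 |
| Simulation, 200,000 trials, pairwise t-tests, 36 per arm | 0.174 |
| Independent tests, for reference: 1 − 0.9² | 0.19 |
| Bonferroni upper bound: 0.10 + 0.10 | 0.20 |

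In the same simulation a single test rejected in 0.100 of trials and the two statistics correlated at 0.498, so the set-up behaves as intended.

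**4. Chance of at least one false claim of benefit.** Counting only the favourable tail, 1 − Φ₂(1.645, 1.645; ρ = 0.5) = 0.0878. One test gives 0.10 / 2 = 0.05. The ratio is 0.0878 / 0.05, about 1.76.

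**5. What familywise control at 0.10 would take, for scale.** Dunnett needs a critical z of 1.916, about 0.055 per comparison. Power at 36 per arm then falls from 80.7% to about 72%, and 80% power needs about 44 evaluable per arm. With ordered testing the first comparison stays at 0.10 and keeps its 80.7%.

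**The case against.** The strongest reply concerns context. The sentence in Protocol 9.4.11 stands in the interim-analysis section and is a conclusion drawn from the absence of planned changes after interim looks. Nothing in that section mentions doses. A reader might infer that the protocol knowingly claims familywise control across the two regimens; the sentence does not support that, because its argument concerns interim looks only. What remains is that its conclusion is worded without that limit. It speaks of the overall alpha of the primary analysis, and for two tests at 0.10 each that figure is wrong even if no interim look takes place.

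The second reply is that unadjusted testing suits this trial. It is Phase 2, the alpha is 0.10, the sample size is described as empirically chosen, and the results serve an internal decision. Protocol 4.3 includes the lower regimen to assess dose-dependent effects and inform later dosing. No rule declares success if either dose is significant. SAP 3.3 and 3.5 disclose the separate tests openly, and Protocol 9.4.5(d) had already named both comparisons. All of this stands. A reader might infer that the plan must adjust, or that the primary analysis is invalid; the documents support neither.

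Third, 0.175 counts results in which imsidolimab looks significantly worse than placebo. That is correct. The figure that matches the harm described, a dose looking effective by luck, is 0.088, and the two should be given together.

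Finally, no calculated figure in either document is in error. The fault lies in how the error rate is described.

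**Conclusion.** The point holds as a correction to how the error rate is stated. The 0.10 is a per-comparison level. Across the two primary tests the familywise rate under the global null is about 0.175 two-sided, and about 0.088 for a false claim of benefit, against 0.05 for one test.

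These figures assume that neither regimen has an effect, that evaluable numbers are equal across arms (correlation 0.5), and that the test statistics are approximately normal or t. Unequal dropout would shift the correlation somewhat. The Bonferroni bound of 0.20 holds whatever the correlation. The figures do not cover the effect, if any, of interim looks at the primary endpoint, which is a separate question.

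The consequence is moderate: the trial's design, sample size and power are unaffected, but the plan states an overall property that the design does not have.

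**What to change.** **Protocol 9.4.11.** Replace the statement about overall alpha with one saying that two-sided 0.10 applies to each dose-versus-placebo comparison. If the sponsor wishes to keep the argument about interim looks, it should be confined to them.

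**SAP 3.5.** Say that no adjustment is made for the two comparisons, rather than that none is needed. Add that, if neither regimen works, the chance of at least one significant result is about 0.175 two-sided and of at least one false claim of benefit about 0.088. The Week 16 results given to management can then be read against those rates.

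The cost is wording in two documents. Conduct, sample size and power do not change; the only downside is that the stated error rate looks less favourable.

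**Optional.** If the sponsor wants the familywise rate held at 0.10, a prespecified testing order achieves it: the second regimen is tested at 0.10 only if the first is significant. The first comparison keeps its 80.7% power, but a claim for the second regimen then depends on the first. Dunnett avoids that dependence at the cost of power, about 72% per comparison at the planned size.

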## 10 SUPPORTING DOCUMENTATION AND OPERATIONAL CONSIDERATIONS

### 10.1 REGULATORY, ETHICAL, AND STUDY OVERSIGHT CONSIDERATIONS

After reading the protocol, each Investigator will sign the protocol signature page and send a copy of the signed page to AnaptysBio or representative. The study will not start at any study site at which the Investigator has not signed the protocol.

